4.5. Withdrawal Criteria

Every effort should be made to keep subjects in the study. The reasons for subjects not completing the study will be recorded.

The following **will** require withdrawal from the study:

- AE, which, in the opinion of the investigator precludes effective participation of the subject or poses a safety concern
- Elevation of liver function test results meeting any of the liver stopping criteria (see Section 6.3.6)
- Severe allergic/hypersensitivity reaction that is considered by the investigator to be attributable to randomized study medication or without a likely alternative etiology (see Section 6.3.9.3)
- Confirmed acute or chronic pancreatitis (see Section 6.3.9.4)
- Confirmed medullary thyroid cancer (see Section 6.3.9.6)
- Recurrent severe hypoglycemia or recurrent nocturnal hypoglycemia during the Treatment Period posing a potential risk to the subject, as judged by the investigator
- Pregnancy or intention of becoming pregnant
- Major protocol deviation if withdrawal from the study is mandated by the medical monitor (the investigator should discuss the protocol deviation with the medical monitor before withdrawing study medication)
- GSK-defined Sentinel Event. The medical monitor will advise the investigator if an SAE meets the criteria of a true Sentinel Event (e.g., without a clear alternate etiology) for which withdrawal is required (see Section 6.3.7.3)

In addition, a subject may be withdrawn from the study for the following reasons:

- FPG >270 mg/dL (15.0 mmol/L) at least 8 weeks after randomization on 3 consecutive days (by blood glucose meter), which is confirmed by a central laboratory (to be done within 2 weeks of the home glucose monitoring). Continuation of the subject will be at the discretion of the investigator after consultation with the medical monitor
- Lost to follow-up
- Study closed/terminated or investigator site closed (where subject transfer to another site is not possible)
- Subject decision (reason to be documented in the electronic case report form [eCRF], if specified by the subject)
- Investigator discretion

Note: Use of a prohibited medication constitutes a protocol deviation. Continuation of the subject in the study will be discussed with the medical monitor, and the decision of continuation or withdrawal will be documented.

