4. ANALYSIS POPULATIONS

Population	Definition / Criteria	Analyses Evaluated
Full Analysis (FA)	
 • Comprise of all subjects randomly assigned to treatment. • Randomly assigned subjects who do not receive any study treatment will also be included. • The subjects in the FA Population will be analyzed according to randomized treatment. 	
 • Study Population • Efficacy
Per-Protocol (PP)	
 • Comprise of all randomized (FA Population) subjects who complete study procedures through Week 26 or beyond. • The subjects in the PP Population will be analyzed according to randomized treatment. 	
 • Supportive Efficacy Analysis
Safety	
 • Include all subjects who receive at least 1 dose of randomized study medication. • The subjects in the Safety Population will be analyzed according to the treatment received. 	
 • Safety • Study Population

NOTES :

- Please refer to Appendix 14: List of Data Displays which details the population to be used for each displays being generated.

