8.1.2. Key Secondary Efficacy Endpoints

8.1.2.1. Proportion of Subjects Who Do Not Meet Prespecified Criteria for Severe, Persistent Hyperglycemia through Week 26

For this key secondary endpoint, subjects who do not meet prespecified criteria for severe, persistent hyperglycemia through Week 26 will be defined operationally as those subjects treated with once-weekly albiglutide that are able to replace prandial insulin without lispro re-introduction through Week 26. Note: For lispro re-introduction through Week 26 the time window is defined up to Week 25.

Proportion of subjects that are able to discontinue insulin lispro at Week 4 and do not meet prespecified criteria for severe, persistent hyperglycemia through Week 26 will be summarized descriptively for all the Albiglutide + Insulin Glargine arm subjects and for

subgroups of baseline HbA_{1c} category (<8.0%, ≥8.0%), region, (<65 years versus ≥65 years), current use of metformin (Yes, No) in the FA population. The 95% confidence interval of the proportions of subjects will be provided.

The insulin lispro that was re-introduced to albiglutide subjects will be characterized. Summary statistics for the number of injections, total dose, and time-to-re-introduction will be presented.

Additional exploratory analyses to identify potential risk factors for lispro re-introduction will be investigated. Potential risk factors include: baseline HbA_{1c}, baseline HbA_{1c} category, age, age category, metformin-use, duration of diabetes, weight, BMI, BMI category, time in insulin (at baseline), baseline HbA_{1c}, and total insulin dose at baseline. Time in insulin (at baseline) is defined as the earliest start date of prior insulin medications taken minus the date of first date of randomized study medication, plus 1.

8.1.2.2. Percentages of Subjects with Severe or Documented Symptomatic Hypoglycemia through Week 26

The percentage of subjects with severe or documented symptomatic hypoglycemia will be summarized descriptively by treatment and analyzed using a Cochran-Mantel-Haenszel (CMH) test, stratified by baseline HbA_{1c} category, region, age category (<65 years versus ≥65 years), current use of metformin (Yes, No) in the FA population.

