As supportive analysis, logistic regression models adjusting for baseline HbA_{1c} category, region, age category and current use of metformin will be used to quantify the treatment effects. Odds ratio for treatment and the associated confidence interval will be used to estimate the treatment difference.

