8.1.3.4. Proportion of Subjects Achieving HbA_{1c} <6.5% at Week 26 and over Time

Proportion of subjects achieving HbA_{1c} target values of <6.5% at Week 26 and over time will be analyzed and summarized in a similar manner as specified in Section 8.1.3.3.

8.1.3.5. Incidence and Time to Meeting Prespecified Criteria for Severe, Persistent Hyperglycemia through Week 26

In this treat-to-target study design, subjects may be withdrawn if they have severe and persistent hyperglycemia. Meeting prespecified criteria for severe, persistent hyperglycemia at week 26 will be defined operationally as being withdrawn due to lack of efficacy as recorded on the Treatment Discontinuation and Study Conclusion eCRF pages. Proportion of subjects who meet prespecified criteria for severe, persistent hyperglycemia at Week 26 will be summarized and analyzed in a same manner as described in Section 8.1.2.2.

The time to meeting prespecified criteria for severe, persistent hyperglycemia through Week 26 will be calculated as the number of days between the date of first dose of randomized study medication and the date of meeting prespecified criteria, persistent hyperglycemia, plus 1. Subjects who do not meet the criteria will be censored at the date of the Week 26 visit or the date of the early termination visit if the subject terminated the study early. Kaplan-Meier estimates of the median time to meeting the criteria and 95% confidence interval for each treatment group will be presented. The treatment difference will be assessed using a log-rank test. The proportion of subjects meeting the criteria up to Week 26 (Day 182) based on Kaplan-Meier estimates will be displayed in the summary table. Kaplan-Meier curves of the times to meeting the criteria for each treatment group will be presented.

The analysis will be performed on FA population and all data will be listed.

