2.31	FA		Proportion of Subjects Treated with Once-weekly Albiglutide That Are Able to Totally Replace Prandial Insulin without Re-introduction of Inuslin Lispro through Week 26		

Efficacy: Tables					
No.	Population	IDSL / TST ID / Example Shell	Title	Programming Notes	Deliverable [Priority]
2.32	FA		Summary Characteristics of Albiglutide-treated Subjects by Prescribed Lispro Re-introduction Status (Albiglutide-treated Subjects Only)		
2.33	FA		Summary Statistics of Prescribed Total Lispro Daily Dose for Subjects Taking Re-introduced Lispro by Visit (Albiglutide-treated Subjects Only)		
2.34	FA		Summary of Number of Lispro (Prescribed) Injections per Day by Visit (Albiglutide-treated Subjects Only)		
Severe or Documented Symptomatic Hypoglycemia					
2.41	FA		Summary of Subjects with Severe or Documented Symptomatic Hypoglycemia through Week 26 by Baseline HbA1c Category, Age Category, Region, and Current Use of Metformin		
2.42	FA		Percentages of Subjects with Severe or Documented Symptomatic Hypoglycemia through Week 26		
2.43	FA		Percentages of Subjects with Severe or Documented Symptomatic Hypoglycemia through Week 26 – Excluding Early Withdrawals		
Change and Percent Change from Baseline in Body Weight					
2.51	FA		Analysis of Change from Baseline in Body Weight (Kg) by Visit		
2.52	FA		Analysis of Percent Change from Baseline in Body Weight (Kg) by Visit		
2.53	FA		Summary Statistics for Body Weight (Kg) by Visit		
2.54	FA		Summary Statistics for Percent Change from Baseline in Body Weight (Kg) by Visit		
Prescribed Insulin Dose and Number of Injections					

Efficacy: Tables					
No.	Population	IDSL / TST ID / Example Shell	Title	Programming Notes	Deliverable [Priority]
2.61	FA		Analysis of Prescribed Total Daily Insulin Dose (IU) at Baseline, Week 4, Week 5, Week 10, Week 18 and Week 26		
2.62	FA		Analysis of Body Weight Adjusted Prescribed Total Daily Insulin Dose (IU/Kg) at Baseline, Week 4, Week 5, Week 10, Week 18 and Week 26		
2.63	FA		Analysis of Prescribed Total Daily Basal Insulin (Insulin Glargine) Dose (IU) at Baseline, Week 4, Week 5, Week 10, Week 18 and Week 26		
2.64	FA		Analysis of Body Weight Adjusted Prescribed Total Daily Basal Insulin (Insulin Glargine) Dose (IU/Kg) at Baseline, Week 4, Week 5, Week 10, Week 18 and Week 26		
2.65	FA		Analysis of Prescribed Total Daily Bolus Insulin (Insulin Lispro) Dose (IU) at Baseline, Week 4, Week 5, Week 10, Week 18 and Week 26		

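### Subjects who withdraw without a recorded event are, by implication, scored as free of hypoglycemia through Week 26, and the only alternative table excludes early withdrawals

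*SAP*

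**What the plan says.** SAP 8.1.2.2 treats the endpoint as a yes/no outcome per subject: "The percentage of subjects with severe or documented symptomatic hypoglycemia will be summarized descriptively by treatment and analyzed using a Cochran-Mantel-Haenszel (CMH) test". The test is stratified by baseline HbA1c category, region, age category and metformin use, the last of these worded "current use of metformin (Yes, No) in the FA population". SAP Section 4 defines that population as follows: "Comprise of all subjects randomly assigned to treatment". The supportive analysis uses the same binary outcome: "logistic regression models adjusting for baseline HbA_{1c} category, region, age category and current use of metformin will be used to quantify the treatment effects".

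SAP Appendix 14 lists three tables for this endpoint. Table 2.41 is a summary by stratification factor, Table 2.42 gives the percentages, and Table 2.43 is titled "Percentages of Subjects with Severe or Documented Symptomatic Hypoglycemia through Week 26 – Excluding Early Withdrawals".

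Protocol 4.5 ties stopping study medication to leaving the study. Among the reasons that make withdrawal mandatory it lists "Recurrent severe hypoglycemia or recurrent nocturnal hypoglycemia during the Treatment Period posing a potential risk to the subject", as judged by the investigator. Protocol 4.5.1 adds one follow-up visit four weeks after withdrawal.

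SAP 8.1.2.2 gives no rule for a subject who leaves without an event. SAP 8.1.3.3 does give a reason-based rule for missing HbA1c in the responder endpoint, and the missing-data analyses in SAP Appendix 6 concern the primary endpoint only.

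**The concern.** A percentage through Week 26 is a 26-week risk only if everyone is observed for 26 weeks. A subject who leaves at Week 3 without an event stays in the denominator and adds nothing to the numerator for the remaining 23 weeks. Both arms are then understated. If one arm loses more subjects, or loses them earlier, it looks better for that reason alone.

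Table 2.43 is not a sound check on this. Some withdrawals are required because of hypoglycemia, so excluding early withdrawals can select on the outcome being compared, and can take more subjects from the arm with more hypoglycemia.

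At stake is the claim of less hypoglycemia with albiglutide, which the protocol lists as a key secondary objective. The formal weight of the test is unclear. The numbered order in SAP Appendix 10 omits this endpoint, while the diagram that follows appears to show it as key secondary endpoint 1, ahead of body weight and insulin dose. The two must be reconciled. If the diagram governs, an inflated error rate here would pass to the tests below it.

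**Working it through.** **The plan's own figures.** No rate, effect or power is stated for hypoglycemia, so there is nothing to reproduce for this endpoint. The arm size used below comes from the primary endpoint and does reproduce: 2 × (1.960 + 1.282)² × 1.2² / 0.3² gives 337 completers per arm after rounding up; 337 / 0.85 gives 397 per arm, or 794 in total.

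**Inputs**
- From the documents: 397 randomized per arm and 15% overall dropout (SAP Appendix 12). In Study GLP108486, adverse events led to withdrawal of active treatment in 5% of albiglutide and under 1% of lispro subjects (SAP 11.6.3.2), a gap of about 4 points.
- Assumed: full 26-week risk p of 30%, 50% or 70%, equal in both arms; constant hazard; withdrawal unrelated to the event; 17% versus 13% withdrawn (4-point gap) or 20% versus 10% (10-point gap), each averaging 15%; withdrawal either uniform over 26 weeks or all at Week 4; observation ending at withdrawal. If events reported at the four-week follow-up visit also count, the loss is smaller.

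**Table 2.42.** Let λ = −ln(1 − p).
- A subject withdrawn at a uniform time has expected observed risk 1 − p/λ.
- A subject withdrawn at Week 4 has observed risk 1 − (1 − p)^(4/26).
- The observed percentage is (1 − d) × p + d × (observed risk), where d is the share withdrawn. The bias between arms is the withdrawal gap times the loss, where loss = p − observed risk.

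Example at p = 50%, uniform timing: λ = 0.693, observed risk 1 − 0.5/0.693 = 0.279, loss 0.221. Albiglutide shows 50 − 17 × 0.221 = 46.2%, lispro 50 − 13 × 0.221 = 47.1%, a spurious 0.9 points.

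| p | Loss, uniform | Bias, 4-point gap | Bias, 10-point gap | Loss, Week 4 | Bias, 4-point gap | Bias, 10-point gap |
|---|---|---|---|---|---|---|
| 30% | 0.141 | 0.6 | 1.4 | 0.247 | 1.0 | 2.5 |
| 50% | 0.221 | 0.9 | 2.2 | 0.399 | 1.6 | 4.0 |
| 70% | 0.281 | 1.1 | 2.8 | 0.531 | 2.1 | 5.3 |

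Biases are in percentage points and favour the arm with more withdrawals. With 397 per arm and an unstratified two-proportion test at two-sided 0.05, the false-positive rate is 5.4% to 9.5% at the 4-point gap and 7.3% to 33.8% at the 10-point gap.

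With equal withdrawal (15% in each arm) and no true difference, there is no bias between arms; each arm is understated, for example 46.7% instead of 50%. With true risks of 40% and 50% and uniform timing, equal withdrawal shrinks the difference from −10.0 to −9.4 points, and 20% versus 10% withdrawal moves it to −11.5.

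**Table 2.43.** Excluding withdrawals unrelated to the event leaves p unchanged under these assumptions. Excluding a share h of an arm who all had events turns p into (p − h)/(1 − h). Suppose 1% to 2% of lispro subjects and no albiglutide subjects are withdrawn for hypoglycemia. At p = 30% and h = 2%, lispro falls to 0.28/0.98 = 28.6%, a drop of 1.4 points. At p = 70% and h = 1%, it falls to 0.69/0.99 = 69.7%, a drop of 0.3 points. The shift of 0.3 to 1.4 points goes against albiglutide, opposite to the shift in Table 2.42 when albiglutide has more withdrawals.

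**The case against.** The strongest reply is that follow-up time is not ignored. SAP 8.3.5 and 11.5.4 define an incidence rate as subjects with the event over person-time, and 8.3.5.1 reports it per 100 person-years by American Diabetes Association category and arm. Tables 3.76 to 3.79 add exposure-adjusted models, with severe and documented symptomatic events modelled separately. This stands as mitigation. But those analyses use the Safety Population and on-therapy events, with a window that SAP Appendix 4 defines differently for the two arms. None models the combined severe-or-documented-symptomatic outcome or gives its 26-week risk in all randomized subjects.

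The size is also modest and rests on assumptions. The planning figure is a single 15%; the 5% versus under 1% concerns adverse-event withdrawals in one earlier study and is not a forecast of total withdrawal here. With 397 per arm and risks of 30% to 40% against 40% to 50%, the 95% confidence half-width is about 6.6 to 6.9 points, well above the bias at a 4-point gap. This stands too.

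Kaplan-Meier is no cure-all. Mandatory withdrawal covers recurrent nocturnal hypoglycemia, which may be asymptomatic or probable symptomatic and so not a qualifying event. Censoring such subjects would be informative. This stands and shapes the fix.

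SAP 8.1.3.5, which plans "Kaplan-Meier estimates of the median time to meeting the criteria" for severe, persistent hyperglycemia, shows only that the method is already in the plan. That endpoint is defined as incidence and time, and its proportion is analyzed in the same crude way as hypoglycemia.

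Finally, Table 2.43 is known only by its title; its programming notes are blank, so its exact exclusion rule is inferred.

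**Conclusion.** The point holds in limited form. Subjects who leave without a recorded event are non-events for time nobody observed. The SAP does not state this rule; it follows from the all-randomized denominator and the binary analysis. The resulting bias between arms is about 0.6 to 2.1 points at an assumed 4-point withdrawal gap, given constant hazard, withdrawal unrelated to the event and assumed risks of 30% to 70%. Table 2.43 can err in the opposite direction.

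Three stronger readings might be inferred, and the documents support none of them.
- That all withdrawn subjects are scored event-free: anyone with a qualifying event before leaving, including a subject withdrawn because of it, counts as an event in Table 2.42.
- That the truth must lie outside Tables 2.42 and 2.43: because they can err in opposite directions, it may well lie between them. Bracketing is only not guaranteed.
- That the plan expects unequal total withdrawal: it cites adverse-event withdrawals in one predecessor study and plans on one common rate.

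This is a worthwhile, inexpensive improvement to a key secondary analysis. It does not invalidate the planned test.

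**What to change.** Keep Table 2.42 as the planned analysis and state in SAP 8.1.2.2 how subjects who leave without an event are scored. Then:

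1. Add, as the main sensitivity analysis in the FA Population, the Kaplan-Meier risk of a first severe or documented symptomatic event at Day 182, censored at withdrawal. Report the arm difference with its 95% confidence interval and a log-rank test stratified by the same factors as the CMH test, including region.
2. Because censoring may be informative, add a version that counts any subject withdrawn for hypoglycemia as an event.
3. Drop Table 2.43, or label it descriptive only.

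The cost is one or two extra tables from event dates already collected, using methods the SAP already specifies elsewhere. The downside is that the first analysis assumes non-informative censoring, which the second is there to test. Separately, reconcile the numbered order and the diagram in SAP Appendix 10 so that the formal standing of this endpoint is clear.

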6.3.1. Hypoglycemic Events

Specific criteria for monitoring hypoglycemic events have been designed to ensure subject safety and to closely monitor hypoglycemia.

At each visit through the end-of-treatment visit (Visit 9; Week 26), subjects should be trained on the signs and symptoms of hypoglycemia (e.g., hunger, confusion, dizziness, anxiety, increased heart rate, visual disturbances), including nocturnal hypoglycemia (i.e.,

nightmares; night sweats; tired, irritable, or confused upon awakening), as well as the common causes of hypoglycemia. Subjects should also be educated on appropriate methods to help prevent hypoglycemia (i.e., strictly observe nutritional guidance from the physician or study site staff, consume small snacks before intense exercise, promptly communicate with the study site on “ill days” for additional guidance). It is also particularly important to advise subjects to contact the study site before any potential dietary change, as this may necessitate a change in insulin doses to avoid the development of hypoglycemia. Subjects should also be educated on how to treat hypoglycemia (e.g., oral glucose treatment with simple carbohydrates).

Subjects will be asked to report hypoglycemic events that occur between study visits using a diary. In this study, hypoglycemic events are defined according to recommendations by the American Diabetes Association and The Endocrine Society Workgroup on Hypoglycemia [Sequist, 2013]. To aid correct classification and treatment of hypoglycemic events, subjects should be instructed to repeat SMBG measurements ≤ 70 mg/dL (≤ 3.9 mmol/L).

Severe Hypoglycemia

- Severe hypoglycemia is an event requiring assistance of another person to actively administer carbohydrates, glucagon, or take other corrective actions. Plasma glucose concentrations may not be available during an event, but neurological recovery following the return of plasma glucose to normal is considered sufficient evidence that the event was induced by a low plasma glucose concentration

Documented Symptomatic Hypoglycemia

- Documented symptomatic hypoglycemia is an event during which typical symptoms of hypoglycemia are accompanied by a measured plasma glucose concentration ≤ 70 mg/dL (≤ 3.9 mmol/L)

Asymptomatic Hypoglycemia

- Asymptomatic hypoglycemia is an event not accompanied by typical symptoms of hypoglycemia but with a measured plasma glucose concentration ≤ 70 mg/dL (≤ 3.9 mmol/L)

Probable Symptomatic Hypoglycemia

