2.2. Study Objectives and Endpoints

Objectives	Endpoints
Primary	

 To evaluate the glycemic effectiveness of once-weekly albiglutide as replacement of prandial insulin in subjects with T2DM receiving basal-bolus insulin therapy 	
 Change from Baseline in HbA_{1c} at Week 26
Key Secondary	

 To determine the proportion of subjects treated with once-weekly albiglutide that are able to replace prandial insulin without the need for re-introduction of insulin lispro 	
 Proportion of subjects treated with once-weekly albiglutide that are able to discontinue insulin lispro at Week 4 and do not meet prespecified criteria for severe, persistent hyperglycemia through Week 26

 To demonstrate a significant difference in the frequency of hypoglycemic events between treatment groups 	
 Percentage of subjects with severe or documented symptomatic hypoglycemia through Week 26

 To demonstrate a significant difference in body weight between treatment groups 	
 Change from Baseline in body weight at Week 26 and over time

 To demonstrate a significant 	
 Prescribed total daily insulin dose at Week 26

[figure not shown]
Objectives	Endpoints
reduction in total daily dose of insulin between treatment groups	
Supportive Secondary	

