8.3.2.1. General Adverse Events Summaries

Summaries of the number and percentage of subjects with AEs and the total number of AEs will be provided by treatment group overall and at the SOC and PT level for the following time periods:

- 1) On-therapy and post-therapy combined period
- 2) Pre-therapy (includes hypoglycemia events)
- 3) On-therapy
- 4) Post-therapy

In addition, on-therapy Adverse events will be presented by time intervals of onset (<=12 weeks, >12 - <=26 weeks) and by treatment group; the on-therapy non-serious AEs will be summarized by treatment group.

An additional on-therapy AE summary will also be provided following government clinical register format; these summaries will include the AEs of hypoglycemia event.

A by-subject listing of all AEs will also be presented.

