8.3.5.1. Hypoglycemic Events

Hypoglycemic events merit special attention in the development and study of drugs for the treatment of T2DM since they are often related to the efficacy of a compound. In order to accomplish this, hypoglycemic event data including supplemental hypoglycemic event information not collected on AE eCRF page are reported on a separate hypoglycemic event eCRF page. However, any hypoglycemic event that meets the criteria for a serious AE will also be included in the serious AE summaries.

Analysis of on-therapy hypoglycemic events will include all AEs coded to the preferred term of 'Hypoglycemia'. For on-therapy hypoglycemic events the number and percentage of subjects with events, the number of events, the incidence rate (per 100 person-years) and AE density (per 100 person-years) by the severity of the event defined by American Diabetes Association [ADA], SAE status, relationship to the investigational product, and withdrawal status will be summarized by treatment group. The events will also be summarized according to intervention provided, action taken with regard to background and anti-hyperglycemic medications and onset week and glucose levels. All hypoglycemic events will be classified as severe, documented symptomatic,

asymptomatic, probable symptomatic, or pseudohypoglycemia per the American Diabetes Association criteria) criteria.

The number of events of hypoglycemia with confirmed home blood glucose monitoring < 3.9 mmol/L and/or requiring third party intervention (i.e., severe, documented symptomatic and asymptomatic hypoglycemic events) in 3 monthly intervals (i.e., from Baseline to Week 12, >Week 12 to Week 26) will be summarized by treatment group. The exposure-adjusted event rate will be compared between treatment groups using a Poisson regression model with offset for the person-year, which will include HbA_{1c} stratum, age (<65 years versus ≥65 years), current use of metformin (metformin use versus no metformin use), and region as covariates.

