5. Example SAS code for analysis on FPG change from baseline by baseline FPG tertiles

```
ODS OUTPUT LSMeans= OUTLIBNAME.LSMeans SLICES= OUTLIBNAME.Diffs;
PROC MIXED DATA= INDATA;
  CLASS USUBJID TRT01PN REGION METFORMIN AGEGR1 HBGR1 FPG_TTL
    AVISITN;
  MODEL CHG= FPG_TTL HBGR1 TRT01PN REGION METFORMIN AGEGR1
    AVISITN TRT01PN*AVISITN TRT01PN*FPG_TTL
    FPG_TTL*AVISITN TRT01PN*FPG_TTL*AVISITN /DDFM =KR;
  REPEATED AVISITN/SUB=USUBJID TYPE=UN;
  LSMEANS TRT01PN*FPG_TTL*AVISITN/SLICE=AVISITN CL DIFF;
  ESTIMATE 'Treatment difference at Week 26 for 1st Baseline FPG
  Tertile'
    TRT01PN -1 1
    TRT01PN*AVISITN      0 0 0 0 1 0 0 0 0 -1
```

```
TRT01PN*FPG_TTL*AVISITN 0 0 0 0 1 0 0 0 0 0  
0 0 0 0 0 0 0 0 0 0 -1  
0 0 0 0 0 0 0 0 0 0 /CL ;  
RUN;
```

5. Example SAS code for analysis on exposure-adjusted event rate with Poisson regression model

```
ODS OUTPUT LSMeans= Lsmeans Diffs=Diffs;  
proc genmod data=INDATA;  
  class USUBJID TRT01AN MCRIT2ML HBGR1 AGEGR1 METFMN CTRYGR1;  
  model NUMEVT1=TRT01AN MCRIT2ML HBGR1 AGEGR1 METFMN CTRYGR1/  
d=poisson offset=PYOFFSET;  
  repeated SUBJECT=USUBJID /corrw covb type=exch;  
  LSMEANS TRT01AN/ EXP ILINK E CL DIFF;  
run;
```

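### The hypoglycemia analyses use no measure of prior hypoglycemia, although it is collected before randomization: a missed efficiency, modest for the key secondary endpoint and not an error

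*SAP*

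**What the plan says.** SAP 2.2 lists among the key secondary endpoints "Percentage of subjects with severe or documented symptomatic hypoglycemia through Week 26". Under SAP 8.1.2.2 it is "analyzed using a Cochran-Mantel-Haenszel (CMH) test, stratified by baseline" HbA1c category, region, age category and metformin use. Logistic regression is supportive and takes the same factors: baseline HbA1c category, "region, age category and current use of metformin will be used to quantify the treatment effects".

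For event rates, SAP 8.3.5.1 has the arms "compared between treatment groups using a Poisson regression model with offset for the person-year, which will include" HbA1c stratum, age, "current use of metformin (metformin use versus no metformin use), and region as covariates". The example code in SAP Appendix 11 reads "model NUMEVT1=TRT01AN MCRIT2ML HBGR1 AGEGR1 METFMN CTRYGR1". The term MCRIT2ML is not defined anywhere in the SAP and is not described as event history.

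The history is nevertheless collected:

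- Protocol Table 5 has the glucose meter and e-diary dispensed at Week -4. Protocol 6.3.1 states: "Subjects will be asked to report hypoglycemic events that occur between study visits using a diary". It also requires the investigator to classify each e-diary event.
- Protocol 5.1.1 requires weekly contact throughout Standardization. Hypoglycemic events are assessed at the Week -4 and Week -1 visits (Table 5) and at the Week -3 and Week -2 calls (Table 6).
- Protocol 6.3.11 starts adverse event collection when Standardization starts. One of the summary periods in SAP 8.3.2.1 is "Pre-therapy (includes hypoglycemia events".

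For continuous endpoints, Protocol 8.3.3.2 puts the endpoint's own baseline in the model. Its stated reasons are to reduce variance and to correct chance baseline imbalance.

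**The concern.** Three key secondary endpoints compare the arms: hypoglycemia, body weight and total daily insulin dose. Weight and insulin dose are adjusted for their own baseline; hypoglycemia is not. The subject's recent event history is an obvious candidate predictor of later events. Fixed before randomization, it cannot be affected by knowledge of the assigned treatment in this open-label trial, so adjusting for it introduces no bias. Less hypoglycemia is also the first advantage over intensified basal-bolus insulin that the protocol rationale names after maintained glycemic control. At stake are some precision and power, and protection against a chance imbalance in proneness. The validity of the planned tests is not at stake.

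**Working it through.** **1. The plan's own figure.** The only sample size calculation is for HbA1c noninferiority (Protocol 8.2.1, SAP Appendix 12): margin 0.3, SD 1.2, true difference 0, one-sided 0.025, power 90%.

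n per arm = 2 × (1.960 + 1.282)² × 1.2² / 0.3² ≈ 336.2, so 337. Power at 337 is 0.9006 (normal) or 0.8998 (noncentral t). 337 / 0.85 = 396.5, so 397 per arm and 794 in total. The plan's figures reproduce and this point does not affect them. No power is stated for hypoglycemia.

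**2. What the documents give for hypoglycemia.** The only effect-size information is that earlier albiglutide studies saw 1.5- to 2-fold less symptomatic hypoglycemia (Protocol 1.2), a ratio of about 1/1.5 = 0.67 to 1/2 = 0.50. No event proportion, dispersion or pre/post correlation is given. The inputs in step 3 are therefore assumptions, varied over a range.

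**3. Simulation.** 397 per arm, 1000 runs per scenario.

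- Expected run-in events: exp(m + σu) × 4/26. Expected treatment-period events: exp(m + βA + σv), with A the arm indicator.
- v = ρu + √(1 − ρ²)·e, with u and e standard normal. ρ is the correlation between a subject's log event rates before and after randomization.
- m gives a control-arm proportion of 40%, 55% or 70%. β gives a true 10-point reduction (rate ratios 0.58 to 0.68). σ is 1.0 or 1.5.
- Logistic and robust-variance Poisson models were fitted with and without run-in history (log(1 + count) and any event). Every simulated run-in lasts 4 weeks, so count and weekly rate carry the same information.
- The four planned covariates and dropout were left out.
- Gain in effective sample size = (mean z with history / mean z without)² − 1.

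| ρ | Binary endpoint (logistic) | Event rate (Poisson) |
|---|---|---|
| 0 | 0% | 0% |
| 0.3 | 0-1% | 0-2% |
| 0.6 | 1-5% | 2-16% |
| 0.9 | 2-12% | 7-100% |

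Binary power without history is about 79-87%. The largest rise is about 4 points: 81.6% to 85.3% at 55%, σ = 1.5, ρ = 0.9. In that scenario Poisson power goes from 72.7% to 88.4%.

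**4. Why the binary gain is small.** Only 9-32% of simulated subjects have any run-in event. At ρ = 0.9 the correlation φ between any run-in event and any treatment-period event is only 0.14 to 0.31. The approximation 1/(1 − φ²) gives 1/(1 − 0.14²) = 1.02 and 1/(1 − 0.31²) = 1.11, close to the simulated 2-12%.

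**5. A different event model.** This used gamma-distributed proneness (shape 0.5), 4 events per person-year, rate ratio 0.7 and 15% withdrawal. If proneness is identical before and after randomization, the SE of the log rate ratio falls from 0.117 to 0.099, a variance factor of (0.117/0.099)² ≈ 1.40. The factor drops to 1.09-1.12 at correlation 0.6, 1.02-1.03 at 0.3 and 1.00 at 0. Logistic power rises by about 6 points at correlation 1 and by about 0 at 0.3. The pre/post correlation decides the result.

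**6. CMH cells.** 6 regions × 2 × 2 × 2 = 48 strata, about 794/48 = 16.5 subjects each. Adding a two-level history stratum gives 96, with about 8.3 each.

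**The case against.** The strongest counter-argument is that proneness may not carry over. Standardization dosing follows local labeling and standard of care, and the protocol reserves the Table 3 glargine algorithm for the Treatment Period. After randomization the albiglutide arm halves lispro and then stops it at Week 4, while the control arm is titrated to target. Four weeks on one regimen need not predict 26 weeks on another, and the documents give no data either way. This stands, and it is why the range must start at zero. Even at zero correlation, however, the covariate cost nothing material in the simulations.

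Second, the main test is the CMH. Adding a covariate to a supportive logistic model leaves the CMH p-value unchanged. This also stands, so the SAP must say which analysis is formal.

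Third, the simulations omit the four planned covariates, so the gain over and above them is unknown. This stands as a limit on the size.

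A reader might infer that the large figures, such as a variance factor of 1.40 or Poisson power rising from 72.7% to 88.4%, describe the key secondary endpoint. They do not. They come from the event-rate model, which the SAP places among its safety analyses, and they need proneness that is fully or almost fully persistent. A reader might also take MCRIT2ML to be event history already in the Poisson model. The SAP does not say what it is, so that reading is unsupported too.

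**Conclusion.** The point holds as a missed efficiency. The listed covariates of all three hypoglycemia analyses omit prior events, the data are already collected on the same event definitions, and the protocol's own reasoning for continuous endpoints favors using them.

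It would be wrong to infer that the key secondary test is biased, invalid or seriously underpowered for this reason: the planned tests remain valid, and nothing in the documents supports the stronger reading. In the main simulation the gain is 0-12% in effective sample size for the binary endpoint (at most about 4 power points; about 6 in the gamma model with identical proneness before and after) and 0% to about 100% for the event-rate comparison. All of this rests on assumed event rates, dispersion and pre/post correlation. With no correlation the gain is nil.

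**What to change.** Before database lock, amend SAP 8.1.2.2, SAP 8.3.5.1 and the Poisson code in Appendix 11:

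- Add to the logistic and Poisson models the log of each subject's pre-randomization hypoglycemia rate per week, for the same event class as the outcome, with a small prespecified constant added.
- Divide by the actual run-in length. Repeat HbA1c or FPG testing can extend the run-in by up to 2 weeks (Protocol 4.4), so raw counts are not comparable between subjects.
- Cut off at randomization. The pre-therapy period in SAP Appendix 4 runs to first dose, which may fall after the open-label assignment is known.
- Report the adjusted logistic result also as a standardized risk difference. In logistic regression, adjustment raises power by moving the conditional odds ratio away from the null, not by shrinking its standard error.
- State whether the four-factor CMH or the adjusted logistic model is the formal test. If the CMH stays formal, the gain is confined to the logistic and Poisson estimates.
- Do not add history as a CMH stratum.
- Define MCRIT2ML in the same edit.

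The cost is one derived variable and SAP wording, with no new data and no additional subjects.
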